### 7.2.2 Karolinska Sleepiness Scale

The Karolinska Sleepiness Scale ([Appendix 10](#)) will be administered according to the schedule in [Table 2](#). The Karolinska Sleepiness scale is a self-report scale that measures the subject's drowsiness. It is a 9-point verbally anchored scale, which ranges from 'extremely alert' at one end of the scale to 'extremely sleepy – fighting sleep' at the other end of the scale. Within this study, the scale will be completed by the observer in an exploratory manner.

### 7.2.3 Healthcare Utilization Questions

In order to better understand the healthcare resource burden associated with the management of DS, caregivers will be asked which of the following hospital and community-based healthcare services they had interactions with over the preceding month: emergency room services, ambulance, planned and unplanned hospitalization, family physician services, speech and language therapy, occupational therapy, and physical therapy. This information will be captured in the CRF.

## 7.3 SAFETY ASSESSMENTS

### 7.3.1 Demographics, Medical/Neurological/Epilepsy History, and Pre-Study Medication

Subject demographics (sex, age, height, weight, and BMI), all ongoing conditions and relevant medical history from the past 5 years (including all major hospitalizations and surgeries) as well as the subject's current medical status and current medications will be carried over from the core study.

### 7.3.2 Physical Examinations

Complete and abbreviated physical examinations, including height and weight, will be conducted by the investigator or designee during the study as outlined in [Table 1](#) and [Table 2](#). A complete standard of care physical examination for each subject will be performed and will cover the following body systems: general appearance, skin, eyes, ears, nose, throat, heart, lungs, abdomen, neurological system, lymph nodes, spine, and extremities. An abbreviated physical examination for each subject will cover the following body systems: heart, lungs, and follow up of other systems as appropriate based on last exam and reported AEs.

Any unfavorable findings not present at Visit 12 of the core study considered by the investigator as clinically significant, occurring at any point in the study will be documented in the CRF as an AE.

### 7.3.3 Neurological Examinations

Complete and abbreviated neurological examination will be conducted by the investigator or designee during the study as outlined in [Table 1](#) and [Table 2](#). A complete standard of care neurological examination for each subject will be performed and will cover the following: cranial nerves, muscle strength and tone, reflexes, coordination, sensory function, and gait. An abbreviated neurological follow-up examination for each subject will evaluate any symptoms or systems found to be abnormal and unstable or potentially unstable that might evolve during study treatment, or to investigate any reported or observed AEs.

### 7.3.4 Vital Signs

Vital signs including blood pressure, heart rate, temperature, and respiratory rate will be documented for subjects during study as outlined in [Table 1](#) and [Table 2](#).

### 7.3.5 Laboratory Measurements

Laboratory safety parameters will be analyzed using standard validated methods.

The following parameters will be assessed by the laboratory as described in [Table 1](#) and [Table 2](#), and [Table 9](#):

- Hematology: hemoglobin, hematocrit, erythrocytes, erythrocyte mean corpuscular volume, leukocytes, mean corpuscular hemoglobin, mean corpuscular hemoglobin concentration, neutrophils, lymphocytes, monocytes, eosinophils, basophils and platelets
- Blood Biochemistry: albumin (ALB), alkaline phosphatase (AP), alanine aminotransferase (ALT; SGPT), aspartate aminotransferase (AST; SGOT), bicarbonate, blood urea nitrogen (BUN), calcium (Ca), chloride (Cl), creatinine, creatine kinase, gamma-glutamyl transferase (GGT), globulin, glucose, lactate dehydrogenase (LDH), phosphorus, potassium (K), sodium (Na), thyroid function (T3, T4, and thyroid stimulating hormone [TSH]), total bilirubin, direct bilirubin, total cholesterol, total protein, triglycerides, uric acid.
- Tests of growth and precocious puberty: growth hormone (GH), insulin-like growth factor-1 (IGF-1, low sensitivity), prolactin, luteinizing hormone (LH), follicle stimulating hormone (FSH), testosterone, estradiol

- Whole blood cannabidiol
- Urinalysis: analysis for pH, glucose, ketones, nitrite, protein, bilirubin, urobilinogen, leukocyte esterase, and occult blood. Microscopic analysis will be performed for blood, all cell types, and casts.
- Urine pregnancy test: Urine pregnancy testing will be performed in female subjects of childbearing potential.
- Urine THC panel

The investigator will receive the laboratory report from the central laboratory. After reviewing the report and evaluating any results that are outside the normal range, the investigator must sign and date the laboratory report.

Tests resulting in abnormal laboratory values that have been classified by the investigator as abnormal, clinically significant should be repeated as soon as possible after receiving the laboratory report to rule out laboratory errors.

Any deviation outside of the reference range considered by the investigator as clinically significant (ie, classified as an abnormal, clinically significant value) at any visit will be documented in the CRF as an AE (Section 9).

### **7.3.6 Plasma Sample for Concomitant Antiepileptic Drug(s)**

Plasma samples to ensure that concomitant AEDs dosing is within an acceptable range will be conducted during the study as outlined in Table 1 and Table 2. All samples will be analyzed at study end and do not constitute safety assessments.

### **7.3.7 Electrocardiograms**

Twelve-lead ECGs will be conducted during study as outlined in Table 1 and Table 2 after the subject has been in the supine position resting for  $\geq 5$  minutes. Heart rate, PR duration, QRS duration, QT duration, QTcF (Fridericia's correction formula), and the investigator's overall interpretation will be recorded.

### **7.3.8 Doppler Echocardiography**

Doppler echocardiography will be conducted at a facility with experience for the subject's age during study as outlined in Table 1 and Table 2. Doppler echocardiography uses ultrasound technology to examine the heart or blood vessels. An ECHO uses high frequency sound waves to create an image of the heart while the use of Doppler technology allows determination of the speed and direction of blood flow by utilizing the Doppler effect. Predetermined standard

guidelines on the proper evaluation of certain measurements, as well as abnormality thresholds, were constructed by the Sponsor's IPCAB prior to study initiation. These thresholds are provided in [Table 10](#) (Adverse Events of Special Interest). A manual of proper ECHO technique for sites is provided in a separate document.

### **7.3.9 Tanner Staging**

Tanner Staging ([Appendix 5](#)) will be assessed for subjects >7 years old during the study as outlined in [Table 1](#) and [Table 2](#). Conceptually, pubertal maturation can be described in terms of sequence, timing, and tempo. Puberty consists of a series of predictable events, and the sequence of changes in secondary sexual characteristics has been categorized by several groups. The staging system used most frequently was published by Marshall and Tanner (1969, 1970) and the sequence of changes are commonly referred to as 'Tanner stages'.

### **7.3.10 Columbia-Suicide Severity Rating Scale**

C-SSRS ([Appendix 2](#)) will be assessed during study as outlined in [Table 1](#) and [Table 2](#). The C-SSRS is a validated rating scale that assesses suicidal behavior and ideation. The scale is used to assess and track suicide events and provides a summary measure of suicidal tendency. The C-SSRS version 6/23/10 (Children's Since Last Visit) will be used in this study as appropriate for the age and level of intellectual development.

Subjects who are younger than 7 years chronologically, or who are judged by the investigator not to have the mental capacity to understand the questions as specified on the C-SSRS, will not complete the rating. The investigator should use his/her judgment to substitute intellectually-appropriate questions to probe the tendency for self-harm.

If a subject with the intellectual capacity to complete the C-SSRS has their 7th birthday during the study, use of the C-SSRS should be initiated at subsequent visits.

### **7.3.11 Adverse Events**

For de novo subjects, adverse events will be collected from the time of signing the informed consent form/assent form until the end of the study, including the follow-up clinic visit. For subjects who participated in one of the core studies, adverse events that occur after signing informed consent for this study, but before Visit 1 will be recorded as adverse events in the core study and medical history in ZX008-1503.

Details of the definitions and categorization of AEs, and procedures for the reporting of AEs, are available in Section 8.

Severity and causality of AEs will be evaluated according to the criteria specified in Section 8.2 and Section 8.3, respectively. The observation period for AE reporting is specified in Section 8.4. At the beginning of each visit at the study site, the study personnel will specifically inquire about any AEs that might have occurred since the last study site visit. All AEs will be recorded on the appropriate CRF page.

#### **7.3.12 Behavior Rating Inventory of Executive Function (BRIEF)**

The BRIEF is a standardized, validated rating scale to measure executive function. Age-appropriate versions of the BRIEF (BRIEF-P: 2 to 5 year olds; BRIEF: 6 to 18 year olds; BRIEF-A: 19 to 35 year olds) will be assessed according to the schedule in Table 1 and Table 2. The BRIEF measures multiple aspects of executive functioning; scales include Inhibit (control impulses; stop behavior), Shift (move freely from one activity/situation to another; transition; problem-solving flexibility), Emotional Control (modulate emotional responses appropriately), Initiate (begin activity; generate ideas), Working Memory (hold information in mind for purpose of completing task), Plan/Organize/Organization of Materials (anticipate future events; set goals; develop steps; grasp main ideas), and Monitor (check work; assess own performance).

#### **7.4 APPROPRIATENESS OF MEASUREMENTS**

All of the variables assessed are standard tests or procedures that are commonly used in studies of this type.

## 8. ADVERSE EVENTS

### 8.1 DEFINITIONS

#### 8.1.1 Adverse Events

According to ICH guidelines, an AE is any untoward medical occurrence in a patient or clinical investigation subject administered a pharmaceutical product and which does not necessarily have a causal relationship with this treatment. An AE can, therefore, be any unfavorable and unintended sign (including an abnormal, clinically significant laboratory finding), symptom, or disease temporally associated with the use of a medicinal (investigational) product, whether or not considered related to the medicinal (investigational) product. For de novo subjects, the period of observation for adverse events extends from the time the subject gives informed consent until the end of study. For subjects who participated in one of the core studies, the period of observation for adverse events extends from Visit 1 of ZX008-1503 until the end of study. Adverse events that occur after signing informed consent for this study, but before Visit 1 will be recorded as adverse events in the core study and medical history in ZX008-1503.

Adverse events may include:

- Illness present before core study entry should be recorded in the medical history section of the CRF along with any ongoing AEs that were present at Visit 13 of the core study. These events should only be reported as an AE if there is an increase in the frequency or severity of the condition from the core study
- Exacerbation of seizures is considered an AE if there was an increase in frequency beyond the subject's typical pre-core study fluctuations, or in the event that seizures lengthen in duration in a clinically meaningful way compared with core study baseline, or if a new seizure type emerges
- A clinical event occurring after consent but before IMP administration
- Intercurrent illnesses with an onset after administration of IMP

Adverse events do not include:

- Medical or surgical procedures (the condition that leads to the procedure is the AE, eg, tonsillitis is the AE if a tonsillectomy is performed)
- Situations where an untoward medical occurrence has not taken place. For example:
  - Planned hospitalizations due to pre-existing conditions, which have not worsened

- Hospitalizations that occur for procedures not due to an AE (eg, cosmetic surgery)
- Hospitalizations for a diagnostic procedure where the hospital stay is less than 24 hours in duration or for normal management procedures (eg, chemotherapy)

For laboratory safety parameters, any instances of absolute values being outside the reference range or changes at any visit after study start that are considered by the investigator as clinically significant must be recorded in the CRF as AEs. In addition, at the investigator's discretion, any changes or trends over time in laboratory parameters can be recorded in the CRF as AEs if such changes or trends are considered to be clinically relevant, even if the absolute values are within the reference range.

Laboratory findings do not need to be reported as AEs in the following cases:

1. Laboratory parameters are already beyond the reference range, unless a further increase/decrease can be considered an exacerbation of a pre-existing condition.
2. Abnormal laboratory parameters caused by mechanical or physical influences on the blood sample (eg, hemolysis) and flagged as such by the laboratory in the laboratory report.
3. Abnormal parameters that are obviously biologically implausible (eg, values that are incompatible with life).
4. An abnormal laboratory value that cannot be confirmed after a repeated analysis, preferably in the same laboratory (eg, the previous result could be marked as not valid and should not necessarily be reported as an AE).

### 8.1.2 Serious Adverse Events

A serious adverse event (SAE) is defined as any untoward medical occurrence that at any dose:

1. **Results in death** – The event must be the cause of death for the SAE to meet this serious criterion.
2. **Is life-threatening** – The term “life-threatening” refers to an event in which the subject was at risk of death at the time of the event; it does not refer to an event that hypothetically might have caused death if it had been more severe.
3. **Requires in-patient hospitalization or prolongation of existing hospitalization** – The Sponsor considers “hospitalization or prolongation of existing hospitalization” for at least 24 hours as the defining criterion for an SAE. Hospital admissions for planned

surgery or for normal disease management procedures (eg, chemotherapy) are not considered as defining criteria for SAEs.

4. **Results in persistent or significant disability or incapacity.**
5. **Is a congenital anomaly or birth defect.**
6. **Is medically significant** – A medically significant event is defined as an event that does not meet any of the other 5 SAE criteria, but which is judged by a physician to potentially jeopardize the subject or require medical or surgical intervention to prevent one of the above outcomes listed as an SAE criterion. Anaphylaxis that is successfully treated by administration of epinephrine prior to other sequelae is an example of a potentially medically important event.
  - The most important term should be selected as the criteria for the SAE. Medically significant should be used when none of the other terms apply, for cases in which, had there not been intervention, one of the other SAE outcomes would have likely occurred. For example, anaphylaxis successfully treated with an epinephrine injection would be a medically important event.
  - For the purpose of data collection in this study, a prolonged seizure or series of seizures from which the subject does not regain consciousness between ictal events, that is at least 30 minutes in duration, is termed SE. A single episode of SE in a 24-hour period, regardless of whether rescue medication was administered, should be entered in the AE log as well as in the seizure diary. If two or more episodes occur within 24 hours, each lasting 30 minutes or more, an SAE of SE should be recorded. Hospitalization to manage SE, regardless of the number of episodes, should be reported as an SAE.

Adverse events that do not fall into the above categories are defined as non-serious AEs.

### 8.1.3 Adverse Events of Special Interest

As per ICH guidance ([E2F Development Safety Update Report \[2011\]](#)), the Sponsor has identified the following AESIs for the ZX008 program ([Table 10](#)).

**Table 10. Adverse Events of Special Interest**

Metabolic/Endocrine
1. Elevated prolactin level $\geq 2x$ above the upper limit of normal (ULN)
2. Hypoglycemia – serum blood glucose more than 20% below the glucose level on Study Day -1 value or more than 10% below LLN (reference range 60 – 140 mg/dL)
Neuropsychiatric
1. Suicidal thoughts, ideation or gestures

LLN = lower limit of normal; ULN = upper limit of normal

### 8.1.4 Adverse Events Requiring Hospitalization

If a subject is treated in a medical facility (hospital, emergency room, free-standing clinic) related to the occurrence of any AE, the following data will be collected to model health care utilization in patients with DS: AE/reason for hospitalization/clinic visit; duration of the visit in hours/days; admission to intensive care unit; and name/number of procedures performed, including but not limited to, electroencephalogram, ECG, ECHO, positive emission tomography (PET) scan, magnetic resonance imaging (MRI), x-ray, computed tomography (CT) scan, surgery, and lumbar puncture/spinal tap.

### 8.2 SEVERITY OF ADVERSE EVENTS

The severity of AEs (whether non-serious or serious AEs) is to be assessed by the investigator as follows (Table 11).

**Table 11. Severity Definition of Adverse Eventsa**

Severity	Definition
Mild	A type of AE that is usually transient and may require only minimal treatment or therapeutic intervention. The event does not generally interfere with usual activities of daily living.
Moderate	A type of AE that is usually alleviated with additional specific therapeutic intervention. The event interferes with usual activities of daily living, causing discomfort but poses no significant or permanent risk of harm to the research participant.
Severe	A type of AE that interrupts usual activities of daily living, or significantly affects clinical status, or may require intensive therapeutic intervention.

a Clinical Data Interchange Standards Consortium Study Data Tabulation Model Severity Intensity Scale for Adverse Event Terminology

### 8.3 CAUSALITY OF ADVERSE EVENTS

The causal relationship of an AE to IMP must always be assessed by the investigator. All AEs will be classified as either related or not related to IMP. If a causality assessment is not provided for an AE (including an SAE), that AE will be considered as related to IMP.

The degree of certainty with which an AE is attributed to IMP or an alternative cause (eg, natural history of the underlying disease, concomitant medication) will be determined by how well the event can be understood in terms of:

- Known pharmacology of ZX008
- Clinically and/or pathophysiologically plausible context
- Reaction of a similar nature previously observed with similar products, or reported in the literature for similar products as being product related (eg, headache, facial flushing, pallor)
- Plausibility supported by the temporal relationship (eg, the event being related by time to administration or termination of treatment with IMP drug withdrawal or reproduced on rechallenge)
- The following classifications should be used in categorization of relatedness:
  1. Not Related: Concomitant illness, accident or event with no reasonable association with study drug.
  2. Related: The event follows a reasonable temporal sequence from administration of study drug and is definitive pharmacologically; cannot to be attributed to concurrent disease or other factors or medications. A clinically reasonable response should be observed if the study drug is withdrawn or dose reduced.

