Controlling for multiplicity with a hierarchical testing procedure, all key secondary endpoints were met in both studies, for ZX008 0.8 mg/kg/day and 0.2 mg/kg/day groups (Study 1) and ZX008 0.5 mg/kg/day (Study 1504 Cohort 2). In Study 1, the proportion of subjects achieving a  $\geq 50\%$  reduction from Baseline in CSF was 67.5% for the ZX008 0.8 mg/kg/day group, and 38.5% for the 0.2 mg/kg/day group, with both groups being statistically significantly different from placebo (12.5%;  $P < 0.001$  and  $P = 0.009$ , respectively). In Study 1504 Cohort 2, 53.5% of subjects randomized to ZX008 0.5 mg/kg/day compared to 4.5% of subjects randomized to placebo achieved a  $\geq 50\%$  reduction from Baseline in CSF ( $P < 0.001$ ).

ZX008 was generally well tolerated in both Study 1 and Study 1504 Cohort 2. Though more subjects randomized to ZX008 than to placebo reported TEAEs during the double-blind studies, the percent of subjects with serious TEAEs was similar. Additionally, the adverse events observed in the program were either already known to be associated with fenfluramine, are common to many other antiepileptic drugs being prescribed to these patients, and/or are common to the age group and population studied. Specifically, the most common adverse events seen were diarrhea, fatigue, pyrexia, upper respiratory tract infection, blood glucose decreased, weight decreased, decreased appetite, lethargy and tremor. No valvular heart disease, pulmonary arterial hypertension or abnormal valve structure was observed in any subject at any time during the entire program.

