### 5.6 PRIOR AND CONCOMITANT MEDICATION

All prior and concomitant medication will be collected in the CRF.

All medications taken by a subject after the first administration of IMP are regarded as concomitant medication and must be documented in the CRF, including over-the-counter medication, herbal and vitamin/supplement preparations.

Subjects are required to take at least one concomitant AED throughout the study. During at least the first 6 months of the study, subjects will continue to receive their existing AEDs at the same dose as prior to initiating this study. However, once the subject has been stable on a ZX008 dose for at least 6 months with good seizure control, investigators will be allowed as per typical clinical practice to alter one or more other concomitant AED doses as deemed clinically appropriate. Concomitant AEDs may be withdrawn completely but all subjects must remain on a minimum of 1 concomitant AED plus ZX008. No new concomitant AEDs may be introduced while in this study. All medication dose changes must be documented with a clinical explanation and justification. Concomitant AED dose adjustments outside of these parameters should be discussed with the Medical Monitor prior to initiation.

Non-study medications and therapies that are considered necessary for the subject's welfare and will not interfere with the response to the study medication may be given at the discretion of the investigator, informing the Medical Monitor as soon as possible.

It should be noted for any subject receiving hypoglycemic agents, the investigator should consider diabetic medication changes in the setting of weight loss and hypoglycemia.

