## **8.7 REPORTING OF SERIOUS ADVERSE EVENTS BY INVESTIGATOR TO IEC/IRB**

The timeframe within an IEC/IRB must be notified of a death or an unexpected SAE considered at least possibly related to the IMP is stipulated by each individual IEC/IRB. The investigator is responsible for complying with the requirements for IEC/IRB notification. The investigator will notify the relevant IEC/IRB within the applicable timeframe by forwarding the safety report (eg, MedWatch/CIOMS form) completed by the Sponsor for the notifiable event.

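### Section 8.3 forces a two-way causality call, but its two definitions leave possibly related adverse events in neither category

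*Protocol*

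**What the plan says.** Section 8.3 of the protocol sets a binary scale: "All AEs will be classified as either related or not related to IMP". The two categories are defined as follows.

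- Related: the event follows the drug in a reasonable time sequence and "is definitive pharmacologically; cannot to be attributed to concurrent disease or other factors or medications". A separate sentence adds: "A clinically reasonable response should be observed if the study drug is withdrawn or dose reduced".
- "Not Related: Concomitant illness, accident or event with no reasonable association with study drug".

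The same section tells the investigator to weigh known pharmacology, clinical plausibility, experience with similar products and timing. It also sets a default: "If a causality assessment is not provided for an AE (including an SAE), that AE will be considered as related to IMP".

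Section 8.7 ties notification of the ethics committee to "a death or an unexpected SAE considered at least possibly related to the IMP". The synopsis (Statistical Methods, Safety) plans adverse event summaries by relationship to study drug, with serious events handled in a similar way. Long-term safety and tolerability is the primary objective (Section 2.1).

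**The concern.** A forced two-way scale works only if every event fits exactly one category. Here one category is defined near certainty of causation and the other near certainty of no causation. The ordinary case in this population lies between them: the drug could have caused the event, and so could the epilepsy or another medicine.

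An investigator who applies the Related definition literally must reject it for such an event, and the only box left is Not Related. An investigator who applies the Not Related definition literally must reject that one instead. The result then depends on which definition a site reads as binding. At stake are the level and the consistency of the relatedness summaries in a trial whose primary objective is safety, and the reporting steps that turn on the causality call.

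**Working it through.** No design figure is involved, so the check is a comparison of texts.

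**Step 1. Do the two definitions cover all events?** Take four types of event and apply each definition.

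| Event | Meets Related? | Meets Not Related? |
|---|---|---|
| Drug link pharmacologically definitive, no other cause | Yes | No |
| No reasonable drug link | No | Yes |
| Plausible drug link, plausible other cause | No: it can be attributed elsewhere | No: a reasonable association exists |
| Plausible but not definitive drug link, no other cause found | No: not definitive | No: a reasonable association exists |

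The last two rows fit neither definition, although Section 8.3 requires a choice. The default to Related does not help, because it applies only when no assessment is given.

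**Step 2. Is the third row common here?** All subjects have Dravet syndrome. Section 5.6 states: "Subjects are required to take at least one concomitant AED throughout the study". Section 1.3 describes the adverse events seen so far as already known for fenfluramine, or as ones that "are common to many other antiepileptic drugs being prescribed to these patients, and/or are common to the age group and population studied". The most frequent serious event in the safety update was seizure, in 24/330 subjects (7.3%), where the underlying disease is always an available explanation. Events with competing causes are therefore to be expected.

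**Step 3. Is Section 8.3 consistent with itself?** Its assessment criteria speak of plausibility and of a degree of certainty. The category that they feed asks for near-certainty.

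**Step 4. Where is the causality call used?**

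- Synopsis: the adverse event and serious adverse event summaries by relationship use it.
- Section 8.7: its threshold is at least possible relatedness, a grade that Section 8.3 does not offer.
- Late serious events: Section 8.6 asks for immediate reporting of those considered causally related. Section 8.4 asks for reporting of any that could be associated with the drug, whatever the investigator's causality opinion. The two rules differ.

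**Step 5. Where is it not used?**

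- Section 8.6: on-study serious events go to the sponsor or medical monitor regardless of causality.
- Section 8.6.1: the investigator reports all serious events to the ethics committee.
- Section 8.8: pulmonary hypertension, and valvulopathy found outside study monitoring, are reported within 72 hours with no causality condition.
- Sections 3.7.2, 6.3 (Table 8), 8.9 and 8.9.1 (Table 12): central reading, adjudication, oversight levels and cardiac follow-up do not refer to the relatedness category.

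**Step 6. Can the effect be sized?** Section 1.3 gives 176/330 = 53.3% of subjects with a related event and 8/330 = 2.4% with a related serious event. Both are counts of calls already made. Neither shows how many events had competing causes or how those were coded, so the share that would be Related under a reasonable-possibility definition cannot be derived.

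**The case against.** The strongest reply is that the text does not send possibly related events to Not Related. That category is limited to events with no reasonable association, the listed criteria are plausibility-based, and a missing assessment counts as related. This is correct. The defect is a gap, and coding as Not Related is one foreseeable way to close it, not an instruction.

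The second reply is practical. With 53.3% of subjects already recorded as having a related event, all of them required to take another antiepileptic drug, investigators have plainly not rejected every uncertain event. That also stands. It does not show that the wording is harmless. If many of those events had possible other causes, sites were not applying the definition literally, and up to about 75 centers (Section 3.4) may have done so to different degrees.

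The third reply is that all treatment-emergent and serious events are summarised whatever their cause (Section 10.5.1), so nothing is lost from the database. This is true and limits the harm to the relatedness summaries and the few causality-dependent steps.

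Several stronger readings are tempting and are not supported:

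- A reader might infer that a response to withdrawal is a condition that must be met, which would exclude deaths and irreversible findings. The sentence says only that a response should be seen if the drug is withdrawn or reduced.
- A reader might infer that valve disease and pulmonary hypertension are pushed into Not Related. Section 8.3 does not name them, Section 1.2 acknowledges their link with the drug, and their detection and follow-up do not use the causality call.
- A reader might infer that serious events escape ethics committee review. Section 8.6.1 covers all of them, and Section 8.7 lists deaths separately.
- A reader might take 80 − 8 = 72 subjects with a serious event but no related one as the size of the problem. Nothing shows that any of those events was possibly related, so the figure measures no misclassification.

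**Conclusion.** The point holds as a defect in the definitions. The two categories are not exhaustive, Related is set near certainty, and events with a plausible drug link and a plausible other cause fit neither. The relatedness summaries can be understated, inconsistent between sites, or both. Sections 8.3 and 8.7 use different grades, and Sections 8.4 and 8.6 contradict each other on late serious events.

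The conclusion rests on reading the definitions as written and on such events being common, which Sections 5.6 and 1.3 support. The size of the effect cannot be estimated from the document. Understatement is the likelier direction where sites apply the Related wording strictly, but the interim figures show that they have not always done so.

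**What to change.** In Section 8.3:

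- Define Related as a reasonable possibility that the study drug caused or contributed to the event, including when another cause is also possible.
- Define Not Related as no reasonable possibility, so that the two categories are exhaustive.
- Keep the response to withdrawal or dose reduction as supporting evidence only.

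In Section 8.7, state that at least possibly related means Related. Reconcile Sections 8.4 and 8.6 so that one rule governs late serious events.

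The cost is a paragraph in an amendment and a note in the case report form guidelines. The reported related-event rate may rise. Events coded before and after the change will not be strictly comparable, so the relatedness summaries should note the date of the change. Retrospective re-coding is not asked for: investigators in an open-label trial with interim results already known would be re-judging old events, which brings its own bias.
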